2.1. Study Objectives

2.1.1. Primary Objective

To compare the change from baseline in extent and severity of intra-abdominal adhesions among subjects treated with LB1148 or placebo.

2.1.2. Secondary Objectives

The secondary objectives of this study are to determine the following among subjects treated with LB1148 or placebo:

- Compare time from surgical closure to resolution or appearance, as appropriate, of 1 or more of the components common to gastrointestinal (GI) dysfunction following elective bowel resection with a planned stoma.
- Compare number of hours to GI2.
- Compare number of hours to GI3.
- Compare number of hours to resolution of POI.
- Compare hospital length of stay (LOS, recorded in hours) through Discharge or Day 14 (whichever comes first).
- Compare the incidence of intra-abdominal adhesions following the second surgery among subjects treated with LB1148 or placebo.
- Compare the extent and severity of intra-abdominal adhesions following the second surgery among subjects treated with LB1148 or placebo.
- Compare change from baseline in incidence, extent, and severity of intra-abdominal adhesions among subjects treated with LB1148 or placebo who had adhesions observed at the time of the first surgery.
- Assess the safety and tolerability of LB1148 in subjects undergoing elective bowel resection.

2.1.3. Exploratory Objectives

The exploratory objectives of this study are to determine if LB1148 reduces the:

- Post-operative abdominal pain.
- Incidence of bowel obstruction through 30 days post-operatively.
- Incidence of hospital re-admittance through 30 days post-operatively.
- Volume of blood product transfusions on the day of surgery.

2.2. Study Endpoints

2.2.1. Intra-Abdominal Adhesions

- Incidence of intra-abdominal adhesions as determined by the surgeon.

- Extent and severity of intra-abdominal adhesions as determined by the surgeon using the
- Intra-Abdominal Adhesion Extent and Severity Assessment Worksheet ([Appendix 5](#)).

2.3. Bowel Function

- GI2, defined as the time from the end of surgery (the time the last skin staple or suture was placed by the surgeon) to the time of toleration of solid food (the time a patient finished meal that required chewing and experienced no significant nausea/vomiting for four hours after the solid meal) AND the time to first bowel movement.
- GI3, defined as the toleration of solid food and either first flatus or bowel movement.
- Ability to tolerate a liquid oral diet (time subject is able to sustain oral liquid intake without need for IV fluid administration).
- Ability to tolerate a solid oral diet (time subject is able to ingest solid food without significant nausea/vomiting for four hours).
- Flatus.
- Bowel movement.
- Insertion, reinsertion, and/or removal of nasogastric (NG)/orogastric (OG) tube.
- Nausea with a Verbal Rating Score (VRS) ≥ 3 (moderate to severe).
- Vomiting or retching.
- POI, defined as the inability to tolerate liquid or solids greater than expected post-operative period, confirmed by imaging studies
- Resolution of POI, defined as having resolved when all of the following criteria are met:
 - Absence of nausea AND vomiting for 12 hours without a NG/OG tube
 - Ability to tolerate a solid or liquid oral diet
 - Passage of flatus OR stool over the preceding 24 hours.

2.3.1. Other Endpoints

- Hospital LOS defined as time of admission to time that discharge order is written. NOTE: Subjects may not be discharged until all of the following criteria are met:
 - Passage of stool
 - Ability to tolerate solid food and drink comfortably
 - Adequate oral analgesia
 - Subject's willingness to be discharged.
- Pain values will be evaluated using:
 - Values recorded from the Numeric Pain Rating Scale (NPRS);
 - Analgesia consumption, including totals for opioid use and morphine equivalents;
- The number of subjects with a recorded bowel obstruction;
- The number of subjects with a hospital re-admission, and
- Blood product transfusion volume on the day of surgery.

2.3.2. Safety Endpoints

Safety and tolerability will be assessed based on the incidence and severity of treatment emergent adverse events (AEs), serious adverse events (SAEs), vital signs, clinical laboratory results.

Specific safety sub-analyses will be performed to assess the safety of LB1148 in the following patient populations:

[figure not shown]
- patients who are on chemotherapy;
- patients with a venous port or catheter;
- patients with varicose veins and superficial vein thrombosis;
- patients with varying degrees of obesity;
- patients who are smokers;
- patients with varying degrees of renal function; and
- patient age groups, including 65-80 years old.

INVESTIGATIONAL PLAN

3.1. Overall Study Design and Plan

This is a multicenter, randomized, double-blind, parallel, placebo-controlled, proof-of-concept, adaptive design, Phase 2 study to evaluate LB1148 for return of GI function, reduction of POI and intra-abdominal adhesions in subjects undergoing elective bowel resection with a planned stoma.

Figure 1 Illustration of Study Design for Protocol LBS-POI-201

* Study Day 0 is the day of surgery. Study dosing could occur on Day -1 and/or up to 2 hours prior to surgery on Day 0.

Subjects scheduled for elective bowel resection, aged 18 to 80 years inclusive, will be screened within 42 days of randomization (Study Day -1). Subjects who meet all inclusion and no exclusion criteria, and provide written informed consent, will be stratified by: 1) surgical approach (either minimally invasive technique or laparotomy) and 2) with or without a planned stoma, and then randomized to receive a split oral liquid dose of LB1148 or placebo (polyethylene glycol [PEG], glucose, and electrolytes) in a 1:1 ratio.

All subjects will receive 350 mL of study drug 6-10 and 2-6 hours prior to surgery (Study Day 1/2). Subjects will then undergo the first surgery. At the time of surgical closure, the investigator will determine the incidence, extent, and severity of adhesions using the Intra-Abdominal Adhesion Extent and Severity Assessment Worksheet ([Appendix 5](#)).

Subjects will be assessed for safety and tolerability, including AEs, physical exam, vital signs, clinical lab tests (chemistry, coagulation, and hematology) while in the hospital and on Day 30. Subjects will be monitored for return of bowel function while in the hospital and discharged following tolerance of solid food and first bowel movement.

Within 8 months of enrollment, subjects will undergo a second surgery for the purpose of ostomy take down or other planned abdominal surgery, at which time the surgeon will determine the incidence, extent, and severity of adhesions. If a subject is not ready for the second surgery by 8 months, the investigator may consult with Medical Monitor to obtain window approval.

Unless required for safety reasons or protocol compliance, all subjects, Investigators, and study site personnel will remain blinded to the identity of the treatment from time of randomization until final database lock.

The Schedule of Assessments is provided in [Appendix 1](#) and the study endpoints are in [Section 2.2](#).

3.2. Rationale for Study Design, Control Group, and Perioperative Standardization

Study Design: This is a multicenter, randomized, double-blind, parallel, placebo-controlled, proof-of-concept, adaptive design, Phase 2 study to evaluate LB1148 for return of GI function, reduction of POI and intra-abdominal adhesions in subjects undergoing elective bowel resection with a planned stoma. The study is randomized to control for factors known and unknown between the treatment groups, and neither the Investigator nor the subject will know which treatment the subject will receive in order to avoid any bias in the study assessments.

Control Group: Placebo, superimposed on current standard of care, is an appropriate control for this study.

Perioperative Standardization of Care: There are no internationally recognized perioperative standards of care for general bowel resection subjects. Although the Enhanced Recovery After Surgery (ERAS) Society has provided suggestions for improved perioperative care for GI surgical patients, these standards have been inconsistently adopted by surgical centers ([ERAS website](#)). Often each surgical center has its own, site-specific practices that best fit its patients and standards of care. This has led to heterogeneous perioperative care across sites and countries. To improve the homogeneity of perioperative care in this study and improve the opportunity to detect the effect of treatment, the following standards are being set forth:

- Subjects must receive:
 - Venous thromboembolism (VTE) prophylaxis according to each institute's regional antithrombotic guidelines.
- Subjects must **not** receive:
 - Solid foods consumed for the 8 hours prior to induction of surgical anesthesia;
 - Alternative carbohydrate drinks 8 hours prior to induction of surgical anesthesia; study drug will replace carbohydrate drinks within that time period;

- Anything by mouth for the 2 hours prior to induction of surgical anesthesia (exception: daily oral medication such as anti-hypertensive may be taken with small volume of water as directed by physician), and

3.3. Study Duration and Dates

The total duration for subject participation is up to 10 months (screen through second surgery).

STUDY POPULATION SELECTION

4.1. Study Population

Inclusion and exclusion criteria are provided below. As stated earlier ([Section 3.1](#)), this is an adaptive design study. Currently, 120 subjects are planned for randomization at approximately 15 sites in the United States. Based on the interim analysis results, the adaptive design of this study may allow for up to 200 total subjects enrolled at study completion.

4.2. Inclusion Criteria

Subjects will be eligible for participation in the study only if they meet ALL of the following inclusion criteria:

1. Scheduled to undergo an elective (non-emergent) bowel resection with a planned stoma via laparotomy or minimally invasive technique. This includes any subject in which a resection of the small intestine, colon, or rectum is performed for any elected indication.
2. Planned stoma takedown or other planned abdominal surgery within 8 months of the initial surgery.
3. Willing to perform and comply with all study procedures including attending clinic visit as scheduled and completion of a second surgery for stoma takedown or other abdominal surgery and to determine the presence of intra-abdominal adhesions.
4. Has been informed of the nature of the study (either the subject or their legal representative), agrees to its provisions, and has provided written informed consent.

4.3. Exclusion Criteria

Subjects will not be eligible for participation in the study if they meet ANY of the following exclusion criteria:

1. <18 or >80 years of age.
2. Requires emergency bowel surgery.
3. Has had 1 or more abdominal surgeries, excluding the current, for inflammatory bowel disease, including, but not limited to, inflammatory bowel disease (IBD), Crohn's Disease, or ulcerative colitis.

Note: This does not apply to previous surgery such as hernia repair unrelated to IBD.

4. American Society of Anesthesiologists (ASA) Class 4 or 5.
5. Known inability to take the study drug orally (i.e. complete small bowel obstruction).
6. Has contraindications or potential risk factors to taking TXA. These include subjects with:
 - a. Known sensitivity to TXA

- b. Recent craniotomy (past 30 days)
- c. Active cerebrovascular bleed
- d. Active thromboembolic disease (such as deep vein thrombosis, pulmonary embolism, cerebral thrombosis, ischemic stroke, or acute coronary syndrome)
- e. Acute promyelocytic leukemia taking all-trans retinoic acid for remission induction, or
- f. Continuing use of a combined hormonal contraceptive and or combined hormonal replacement therapy (including combined hormonal pill, patch, or vaginal ring)

7. Has peritoneal carcinomatosis.
8. History of or current seizure disorder.
9. Patients with myeloproliferative disorders.
10. Any other condition that, in the opinion of the Investigator, would preclude the subject from being an appropriate candidate for the study, including severe renal or hepatic impairment.
11. Planned treatment with alvimopan (Entereg®) during study participation period.
12. Planned use of 4% icodextrin (Adept®) or SEPRAFILM during the first surgery.
13. Received any other investigational therapy within 4 weeks prior to Randomization
14. Female subjects of childbearing potential with a positive urine or serum pregnancy test or who are not taking (or not willing to take) acceptable birth control measures (abstinence, intrauterine devices, contraceptive implants or barrier methods) through Day 30.
Additionally, those women who are lactating and insist on breast feeding within 5 days of the last dose of study drug.
15. Known history of radiation enteritis.

STUDY TREATMENTS

5.1. Description of Treatments

5.1.1. Study Drug

LB1148 contains 7.5 g TXA, polyethylene glycol (PEG), glucose, and electrolytes. A dose of 700 mL of LB1148 will be administered orally (refer to [Section 5.2](#)).

5.1.2. Placebo

The placebo contains PEG, glucose, and electrolytes. A dose of 700 mL of placebo will be administered orally (refer to [Section 5.2](#)).

5.2. Treatment Administration

Eating, bowel prep, and drinking will be held 1 hour before and 1 hour after study drug administration.

A total of 700 mL of study drug should be completely consumed orally 2-10 hours prior to induction of surgical anesthesia. Study drug will be provided to subjects in 2 bottles, approximately 350 mL in each bottle:

- Subject will consume the first 350 mL 6-10 hours prior to surgery.
- Subject will consume the second 350 mL 2-6 hours prior to surgery.

5.3. Selection and Timing of Dose for Each Subjects

The 7.5 g dose was chosen for safety and efficacy reasons. The minimally effective concentrations of TXA in the lumen of the small intestine were 45 mM ([Delano et al., 2013](#)) and 56.5 mM ([Chang et al., 2012](#)). LB1148 is formulated at a concentration of 68.2 mM (7.5 g TXA per 700 mL solution).

In preclinical testing, LB1148 demonstrated efficacy when administered 2 hours prior to abdominal surgery. For this study, study drug will be administered 2-10 hours prior to abdominal surgery (refer to [Section 5.2](#) and [Section 6.8](#)). Additional information regarding dose selection, safety, and preclinical efficacy can be found in the LB1148 IB.

The ASA Practice Guidelines for Preoperative Fasting are based on a synthesis and analysis of the current literature, expert and practitioner opinion, open forum commentary, and clinical feasibility data. These Guidelines are recommendations to assist the practitioner and patient in making health care decisions. The guidelines currently read that patients should fast from clear liquids for 2 hours pre-operatively and fast from regular meals for 8 hours pre-operatively ([ASA, 2011](#); [Korpman et al., 2012](#)). This protocol was designed to be in alignment with ASA Practice Guidelines.

5.4. Method of Assigning Subjects to Treatment Groups

Subjects who meet all study criteria for enrollment will be randomly assigned to either the investigational drug (LB1148) or placebo treatment group. Assignment to treatment groups will be determined by a computer-generated randomized sequence using an interactive response system (IXRS). All randomized subjects will be divided between the 2 treatment groups (LB1148 or placebo) in a 1:1 ratio, stratified by: 1) surgical approach (either minimally invasive technique or laparotomy) and 2) with or without a planned stoma.

5.5. Blinding

This is a randomized double-blind study. The subject's coded treatment assignment will be provided to the blinded pharmacist or designee by an IXRS. The randomization code for treatment assignment will be retained by the IXRS.

Unless required for safety reasons or protocol compliance, it is anticipated that there will be little need to unblind a subject's treatment assignment at the site level. Treatment code must not be broken except in medical emergencies when the appropriate management of the subject necessitates knowledge of the treatment randomization. Because no known antidote for LB1148 exists, there should be no medical reason for unblinding at the site.

The Medical Monitor should be contacted if the Investigator requests unblinding a subject's treatment assignment. Emergency unblinding for AEs may be performed through the IXRS. If the treatment code is broken, then the Investigator(s) must document and report it to the Sponsor.

The Sponsor retains the right to break the code for SAEs that are unexpected and suspected to be causally-related to treatment, and that potentially require expedited reporting to regulatory authorities.

The Sponsor or its designee intends to unblind the treatment assignment at the time of the interim analysis; however, the study double blind (subject, Investigator, and/or designated study site team [investigative team]) will remain intact. Care will be taken such that unblinded Sponsor representative will have no contact with the site in regards to any subject data that are not yet collected by the investigative team. Further, the contract research organization (CRO) representatives in direct contact with the investigative team will remain blinded to treatment assignment throughout the study.

5.6. Concomitant Therapy

The subject must not perform any of the following during study participation:

- Receive other medication containing TXA while receiving study drug;
- Receive pancreatic enzyme replacement therapy during the Surgical Period;

- Use a combined hormonal contraceptive and or combined hormonal replacement therapy (including combined hormonal pill, patch or vaginal ring) during the 7 day period prior to Surgery through the 7 day period following surgery;
- Consume solid foods 8 hours prior to induction of surgical anesthesia;
- Receive alternative carbohydrate drinks. Study drug will replace carbohydrate drinks within 8 hours prior to induction of surgical anesthesia.
- Consume anything by mouth (NPO) for the 2 hours prior to induction of surgical anesthesia. (Exception: daily oral medication such as anti-hypertensive may be taken with small volume of water as directed by physician).
- Receive 4% icodextrin (Adept®) or SEPRAFILM during the first surgery
- Use post-operative alvimopan (also known as Entereg®).

Otherwise, there are no restrictions with respect to concomitant therapies for this study. All concomitant medications should be listed in the electronic case report form (eCRF) along with the date therapy was initiated and, if applicable, terminated.

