6.5. Concomitant Medication Assessments

Concomitant medications, including prescription and over-the-counter drugs, will be recorded within 2 weeks prior to randomization through Post-Operative Day 14, and at Hospital Discharge, or study termination, whichever comes first. Additionally, any perioperative surgical preparation that was given or consumed will be documented, including mechanical bowel prep and nutritional supplements (refer to [Section 3.2](#), [Section 5.6](#), and [Section 0](#)).

Blood products administered to the subject will be documented throughout the same timeframe on the Concomitant Medication eCRFs. Documentation will include start and stop dates and reasons for the use.

Unless otherwise specified in the protocol, administration of other concomitant investigational drugs or devices for any indication, other than study drug, is not permitted while on study. Additionally, receiving medication with TXA while taking the study drug is prohibited along with receiving pancreatic enzyme replacement therapy. Any therapeutic or surgical procedures performed during the study period will be documented. Documentation will include information regarding the date(s), indication(s), description of the procedure(s), and/or any clinical or pathological findings.

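### The ban on non-study TXA ends 2-6 h before the first operation, so planned TXA during surgery is not prohibited in either arm

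*Protocol*

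**What the plan says.** Protocol 5.6 lists what a subject must not do while in the study. The TXA item reads "Receive other medication containing TXA while receiving study drug". Section 6.5 states the same limit: "receiving medication with TXA while taking the study drug is prohibited along with receiving pancreatic enzyme replacement therapy".

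The dosing schedule fixes when that limit expires. Section 5.2 places the first bottle 6-10 h before surgery, and for the second says "Subject will consume the second 350 mL 2-6 hours prior to surgery". Section 5.6 also allows nothing by mouth in the last 2 h before induction, apart from daily medication with a little water.

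After the list, 5.6 closes with "Otherwise, there are no restrictions with respect to concomitant therapies for this study".

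The active arm receives 7.5 g of TXA (5.1.1); the placebo contains none (5.1.2). Thrombotic events are of special interest (7.3) and are recorded and followed because TXA affects clotting (7.4). Transfusion volume on the day of surgery is an exploratory objective (2.1.3), and SAP 11.3 gives it a listing only.

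**The concern.** TXA is the active ingredient under test, yet the rule against taking more of it stops before the incision. An anaesthetist or surgeon who plans to give TXA in the operating room breaks no protocol rule. The subject may already have taken 7.5 g, or none, and the team does not know which: 5.5 keeps the code closed except in medical emergencies, and planned use is not one.

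Two readings would suffer. A thrombotic event in an LB1148 subject who also had operating-room TXA could not be assigned cleanly to the study dose, and one in a placebo subject given TXA would no longer represent a subject without TXA. Transfusion volume has the same difficulty, since TXA given in the operating room acts on bleeding directly.

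**Working it through.** **1. When the ban ends.** Inputs: the wording in 5.6 and 6.5, and the schedule in 5.2. The last permitted intake is 2-6 h before surgery. A ban tied to that intake covers 0 h of the operation and 0 h of recovery.

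**2. Whether other text extends it.**
- The lead-in to 5.6 refers to the whole of study participation, but the TXA item carries its own narrower limit and 6.5 repeats it.
- Section 6.5 bars other investigational drugs during the study. Marketed TXA is not caught by that.
- The closing sentence of 5.6 releases whatever the list does not name.
- No other section of the protocol or SAP bars, limits or separately analyses TXA given at or after surgery.

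Planned use is thus allowed by the absence of a rule, not by express permission.

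**3. The other drug and device items in 5.6.**

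| Item | Window | Reaches surgery or later? |
|---|---|---|
| Non-study TXA | while taking study drug | no |
| Pancreatic enzymes | "Receive pancreatic enzyme replacement therapy during the Surgical Period" | yes |
| Combined hormonal products | "during the 7 day period prior to Surgery through the 7 day period following surgery" | yes |
| Icodextrin or Seprafilm | "SEPRAFILM during the first surgery" | yes |
| Alvimopan | "Use post-operative alvimopan" | yes |

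Four of five reach the operation or later. The hormonal item is the most telling: exclusion criterion 6f lists these products among contraindications or risk factors for TXA. The protocol carries that TXA-related precaution to 7 days after surgery, but not a limit on TXA itself.

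**4. Effect on exposure.** As designed, exposure is 7.5 g against 0 g, a difference of 7.5 - 0 = 7.5 g. Let x be an extra dose; the documents give no value, so 1, 2 and 5 g are assumptions.

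| x (assumed) | LB1148 subject, 7.5 + x | Placebo subject, 0 + x |
|---|---|---|
| 1 g | 8.5 g | 1 g |
| 2 g | 9.5 g | 2 g |
| 5 g | 12.5 g | 5 g |

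If a fraction f of placebo subjects receives TXA, the between-arm difference in any TXA exposure falls from 100 points to 100 × (1 - f): 90, 70 and 50 points for assumed f of 10%, 30% and 50%. These figures show direction only and predict nothing.

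**5. How the analysis would treat it.** Section 10.7 counts receipt of a prohibited medication as an important deviation, and SAP 4.1 removes subjects with important deviations from PP. Planned operating-room TXA is not prohibited, so it triggers neither. It would still appear in the concomitant-medication tables by arm (SAP 9) and in the listings (SAP 13).

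**The case against.** The strongest reply is that the rule is deliberate and little follows from it. Section 1.1 says intravenous TXA does not reach therapeutic levels in the bowel lumen, so a ban limited to co-administration fits the mechanism. Windows differ because agents differ, and 5.6 also holds three food and drink items that end by induction; over all eight items, four reach surgery. The surgical team knows the trial tests TXA and can assume exposure. Active thromboembolic disease is excluded, VTE prophylaxis is mandatory, and leg examinations run to Day 14 or discharge. Concomitant medication is recorded (6.5, 6.9), tabulated by arm and weighed in causality (7.12).

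Much of this stands. Uneven windows are not an error in themselves, and recording is not the gap. If planned use were balanced between arms, the randomized comparison would remain valid, as LB1148 added to background TXA. But none of these safeguards prevents stacking, and later causality review cannot restore a placebo group free of TXA.

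Three stronger readings are tempting and unsupported:
- **Biased efficacy.** A reader might infer that adhesion or bowel-function results are contaminated. Section 1.1 points the other way for the intravenous route, and nothing else shows an effect.
- **An exceeded dose limit.** A reader might infer that the cited safety support stops at 7.5 g. Section 1.4 cites 100 mg/kg for 8 days and 1.1 cites larger intravenous doses; neither is presented as a ceiling. A combined dose is not shown to be unsafe.
- **Common practice.** A reader might suppose that operating-room TXA is routine at these sites. The documents do not say so.

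**Conclusion.** The gap is real on the current text: the ban covers none of the first operation, in either arm. Its consequence is limited to attribution of thrombotic events and interpretation of an exploratory, listing-only transfusion volume. The primary endpoint, the bowel-function endpoints and the planned tests are not shown to be affected.

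The size of the clinical effect cannot be given, because the documents state neither the frequency nor the dose of operating-room TXA. The conclusion assumes that the wording in 5.6 and 6.5 is applied literally and that no site procedure outside these documents already bars such use. I rate it optional: a cheap improvement.

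**What to change.** - **Protocol 5.6 and 6.5:** prohibit planned or prophylactic non-study TXA, by any route, from the first study dose through the Surgical Period, which 6.2 identifies as the day of the first surgery. Any longer window is for the sponsor's safety judgment. The 7 days set for hormonal products carry no stated TXA rationale and need not be copied.
- **Rescue:** allow TXA for bleeding, recorded with dose, route and time, and state that it does not count as a prohibited medication under 10.7.
- **Listings:** flag any non-study TXA in the existing concomitant-medication, adverse-event and transfusion listings.

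**Cost.** The text change is a few words in two sections. The eCRF needs dose, route and time fields if it lacks them; 5.6 itself asks only for start and stop dates. Perioperative choice is slightly narrowed, and staff must separate planned from rescue use. Each planned-use case becomes an important deviation and removes one subject from PP: 1/30 = 3.3%, taking the 30 randomized subjects that SAP 4.3 expects as a minimum. Rescue use removes none, and mITT is unchanged.
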